1.2 DRUG PROFILE

Preclinical summary

BI 655066/ABBV-066 (risankizumab) binds with high affinity to human and cynomolgus monkey IL-23, but it does not bind to rat or murine IL-23. There was no binding to IL-12 at the highest concentration (100 nM) tested. Binding to human IL-23 was analyzed in the presence of 50% human serum to assess the potential for non-specific binding. BI 655066/ABBV-066 (risankizumab) does not display interference to binding in the presence of 50% serum.

The primary functional cell assay for the IL-23 antibodies measures their ability to inhibit IL-23 stimulated IL-17 production from mononuclear cells isolated from mouse spleens.

Human, cynomologus, rat and mouse recombinant IL-23 are all capable of stimulating IL-17 release from mouse splenocytes with similar EC50 values. The ability of BI 655066/ABBV-066 (risankizumab) to functionally inhibit both a recombinant and natural form of IL-23 was measured in this system. IC50 values for

BI 655066/ABBV-066 (risankizumab) were equivalently low against recombinant (6 pM) and naturally occurring (1 pM) forms of human IL-23 and lower than the IC50 observed with ustekinumab of 167 pM.

BI 655066/ABBV-066 (risankizumab) did not affect IL-12 at a maximum concentration tested of 33 nM and it did not inhibit IL-12 stimulated IFN- γ production, in contrast to a control antibody against IL-12 p70 that completely inhibited IFN- γ output.

A mouse ear inflammation model ([R11-1273](#)) of *in vivo* efficacy of BI 655066/ABBV-066 (risankizumab) demonstrated 71% inhibition of ear skin thickness, 100% inhibition of ear tissue IL-17 and 94% inhibition of ear tissue IL-22 after 1 mg/kg of BI 655066/ABBV-066. When ustekinumab was studied in the same model, similar levels of inhibition in IL-17 and IL-22 levels were seen at a dose of 1 mg/kg of ustekinumab as with 0.1 mg/kg of BI 655066/ABBV-066. These results suggest that BI 655066/ABBV-066 (risankizumab) may have higher potency than ustekinumab.

Toxicology summary

No adverse findings have been identified in any of the toxicology studies using BI 655066/ABBV-066 (risankizumab).

In the 26 week monkey toxicity study, marginal but transient test article-related decreases in B lymphocytes were noted only at Month 1 in \geq 5mg/kg/week animals (both sexes), but this change was not noted at 3 or 6 month time points. Given the small magnitude of change and the transient nature of the decrease in B lymphocytes, this is not considered an adverse change. Also in the 26 week study, hypospermatogenesis was observed at a low incidence in the testes of \geq 5 mg/kg/week males and correlated with a reduction in testes weights only in 50 mg/kg/week males. Following 8 weeks of recovery, there was no testicular pathology or testis weight effect in 50 mg/kg/week males. The hypospermatogenesis was not considered as an adverse event given the small magnitude of change and no corresponding decrease of epididymal sperm. In contrast, an external expert panel interpreted these findings as normal variations associated with the onset of puberty that were not considered to represent testicular toxicity related to treatment with BI 655066/ABBV-066 (risankizumab). Moreover, a repeat 26 week male fertility study in sexually mature monkeys demonstrated that weekly subcutaneous administration of BI 655066/ABBV-066 (risankizumab) at 50 mg/kg/week for 26 weeks to sexually mature male cyno monkeys produced no BI 655066/ABBV-066 (risankizumab) related effects on reproductive parameters.

The toxicology data suggest BI 655066/ABBV-066 (risankizumab) can be safely administered to humans, as supported by chronic administration to monkeys for up to

26 weeks. The monkey was identified as the most relevant toxicology species with a NOAEL of 50 mg/kg/dose, corresponding to an exposure (combined sex) of 677 µg/mL for the Cmax and 86,250 µg.h/mL for AUC0-168, respectively.

Clinical summary

BI 655066/ABBV-066 (risankizumab) has been studied in a randomized, double blind, single dose trial in a total of 39 patients with moderate to severe psoriasis (Study 1311.1). BI 655066/ABBV-066 (risankizumab) was administered i.v. in ascending doses ranging 0.01 mg/kg to 5 mg/kg i.v., or s.c. in doses of 0.25 mg/kg or 1 mg/kg. After a single i.v. administration, exposure (Cmax and AUC) to BI 655066/ABBV-066 (risankizumab) increased with dose in an approximately dose-proportional manner. The variability and the estimates of the pharmacokinetic parameters after i.v. dosing of BI 655066/ABBV-066 (risankizumab) appears to be in line with other mAbs binding a soluble target. The geometric mean half-life of BI 655066/ABBV-066 (risankizumab) ranged from approximately 20-28 days. The Tmax occurred at approximately 1 to 2 h from start of i.v. infusion in all patients given BI 655066/ABBV-066 (risankizumab).

Mean Psoriasis Area and Severity Index (PASI) scores showed no relevant change over time among placebo treated patients, but showed marked improvements among the BI 655066/ABBV-066 (risankizumab) treatment groups in Study 1311.1. At doses of 0.25 mg/kg and above, all dose groups showed improvement in mean PASI scores of at least 75% from baseline by week 12, which lasted at least until week 20. Similar improvements were observed in both of the BI 655066/ABBV-066 (risankizumab) subcutaneous dose groups.

In a subsequent randomized double-dummy design phase IIb trial, 166 patients with moderate or severe plaque psoriasis were randomly assigned to one of three dose regimens of BI 655066/ABBV-066 (risankizumab) (18/0, 90/90 or 180/180 mg s.c. at weeks 0 and 4) or ustekinumab (45 or 90 mg, per weight, s.c. at weeks 0 and 4). The primary endpoint was PASI 90 at week 12, comparing BI 655066/ABBV-066 (risankizumab) with ustekinumab. In the pre-specified primary analysis of the 90 and 180 mg BI 655066/ABBV-066 (risankizumab) doses (pooled), BI 655066/ABBV-066 (risankizumab) was superior to ustekinumab (PASI 90 77.1% for BI 655066/ABBV-066 (risankizumab) vs 40.0% for ustekinumab [$p < 0.0001$]). Ninety percent of BI 655066/ABBV-066 (risankizumab) patients had sPGA of clear or almost clear compared with 67.5% for ustekinumab. Forty-six percent of BI 655066/ABBV-066 (risankizumab) patients had complete clearing of lesions (PASI 100) compared with 17.5% for ustekinumab. AEs were similar across treatment groups with no drug-related severe or serious AEs. Thus, selective blockade of IL-23p19 with BI 655066/ABBV-066

(risankizumab) was associated with clinical responses superior to ustekinumab in patients with moderate-to-severe plaque psoriasis.

The overall safety profile of risankizumab is consistent with its mechanism of action. Across all indications and doses, the most frequently reported AEs (AEs or serious AEs that received at least 1 dose of risankizumab) were nasopharyngitis, upper respiratory tract infection, headache, and arthralgia. Based on the review of all the risankizumab safety data to date, there are no important identified risks.

For further details see the Investigators Brochure.

2. RATIONALE, OBJECTIVES, AND BENEFIT - RISK ASSESSMENT

2.1 RATIONALE FOR PERFORMING THE TRIAL

The etiology of CD is unknown but data suggests altered immune regulation at the epithelial barrier leading to overproduction of inflammatory cytokines, tissue destruction and aberrant tissue repair ([R13-2231](#)).

Biologic agents targeting TNF α , a cytokine thought to mediate the pathology of CD, have been used extensively for this indication. However, one-third of patients do not respond to anti-TNF agents, and another third of patients have only a transient response ([R13-2268](#), [R13-2267](#), [P13-05746](#), [R13-2264](#), [R13-2266](#), [R13-2265](#)). There remains a high unmet medical need for effective therapies for CD, particularly with a different mode of action that overcomes current treatment limitations.

Among the cytokines involved in CD pathogenesis, data at the genetic, human biology and clinical level strongly suggests the role of IL-23 in this disease ([R13-2625](#); [R12-5152](#)). Analysis of tissue obtained from surgical biopsies or endoscopies has shown that IL-23 and IL-23R are upregulated in the inflamed mucosa of CD ([R12-1009](#)). Data from T cell-driven murine models of colitis support the role of IL-23 in gut pathology ([R11-1269](#); [R11-1271](#)). Ustekinumab, an IL-12/IL-23 p40 antagonist mAb, has shown clinical efficacy in Phase II studies of CD ([R12-5152](#)). Furthermore, the IL-23 p19 antibody MEDI-2070 has shown very promising activity in patients with CD who have failed one or more anti-TNF treatments before ([R15-1973](#)). Finally, BI 655066/ABBV-066 (risankizumab) has shown superior clinical efficacy with comparable safety compared to ustekinumab in a phase II trial in chronic plaque psoriasis, another disease associated with dysregulation of the IL-23 pathway ([P15-03262](#)).

Together, these observations suggest that BI 655066/ABBV-066 (risankizumab) may demonstrate efficacy in this disease.

2.2 TRIAL OBJECTIVES

The purpose of this long term safety extension trial is to provide subjects who responded to treatment with BI 655066/ABBV-066 (risankizumab) in a preceding trial with a long-term treatment option.

The primary objective of the study is to investigate long-term safety of BI 655066/ABBV-066 (risankizumab), in patients with moderately to severely active Crohn's disease, who showed a clinical response or remission on previous treatment with BI 655066/ABBV-066 (risankizumab) and are now receiving long term treatment.

Additional objectives of this study are to further investigate long-term efficacy, tolerability, pharmacokinetics, pharmacodynamics and immunogenicity of BI 655066/ABBV-066 (risankizumab).

Study endpoints are listed in [Section 5.1.1](#).

2.3 BENEFIT - RISK ASSESSMENT

The preclinical and clinical profiles of BI 655066/ABBV-066 (risankizumab) suggest that it profoundly inhibits IL-23 in patients with psoriasis and thus has the potential to address unmet medical need in Crohn's disease, as shown for other IL23 inhibitors before (see [Section 1.2](#) ([R15-1973](#))). Since Crohn's disease is a chronic disease that typically requires long-term treatment, a direct benefit for the individual participants in this study can be assumed, since only such patients will be enrolled that have achieved a clinical response to this compound in the preceding trial 1311.6.

In addition, participation in this study may help to generate a group benefit by providing a new treatment modality for the population of patients with moderate or severe Crohn's disease if BI 655066/ABBV-066 (risankizumab) proves to be successful in treating this disease.

Though there are no serious adverse drug reactions known to be associated with risankizumab therapy, risks of participating in this study include risk of infection and risks related to the trial specific procedures blood sampling, infusion and injection of study medication, and ileocolonoscopy.

Blood sampling, intravenous infusions and subcutaneous injections can cause local bruising, inflammation, and pain. Ileocolonoscopy although generally well tolerated, can be associated with diarrhoea, abdominal pain, perforation, bleeding, effects from anaesthetic medications and infection.

As with any immune modulating agent, BI 655066/ABBV-066 (risankizumab) has the potential to impair immune function resulting in an increased risk of infections. This will be addressed by clinical monitoring for AEs during the treatment and observation periods.

Interferon gamma (IFN- γ) release assay to *M. tuberculosis* will be obtained at visit 1, to exclude or discontinue patients with untreated active or latent TB infection. All patients with negative TB screening at baseline will be re-tested once per year in order to exclude possible active or latent TB infection. Patients having current signs or symptoms of infection or history of serious infection will not be included in the study.

Major adverse cardiovascular events, including myocardial infarction, cerebrovascular accident, and cardiovascular death, have been reported in patients with Psoriasis treated with the anti-IL-12/23 agents, ustekinumab and briakinumab, based on their frequent comorbidities associated with cardiovascular risk. Such an association has not been reported in other diseases and the causal relationship of MACE to treatment with these agents is unclear. The overall risk of MACE in the present study is considered to be low. However, all suspected cardio- and cerebro-vascular events (serious or nonserious) observed in this study will be adjudicated by an independent cardiovascular adjudication committee (CAC) during long-term treatment.

Local reactions to s.c. administered biologic agents are uncommon, and are usually limited to redness, swelling or induration at the injection site. Manifestations of systemic infusion reactions include anaphylaxis, pruritus, hypotension, and respiratory distress. Both local and systemic hypersensitivity reactions were rare in phase II, readily detectable, transient in nature, and manageable with standard medical treatment. No systemic hypersensitivity reactions have been reported with BI 655066/ABBV-066 (risankizumab) to date. Patients will be closely monitored for at least 2 to 3 hours after start of i.v. drug administration whereas 30 minutes to 1 hour after s.c. drug administration for signs of redness, swelling or hardness at the injection site or generalized itching, dizziness or difficulty breathing.

The role of IL-23 in tumor immunity is not well established at this time, but an increased risk of cancer from an IL-23 antagonist, though considered small, cannot be excluded.

Although rare, a potential for drug-induced liver injury is under constant surveillance by sponsors and regulators. Therefore, this study requires timely detection, evaluation, and follow-up of laboratory alterations of selected liver laboratory parameters to ensure patients' safety.

Summary of benefit-risk assessment

The benefit-risk profile is considered appropriate for an experimental therapy at this stage of clinical development. In order to mitigate any safety signals as early as possible, an independent DMC will oversee this study.

The independent external CAC will be adjudicating observed cardio- and cerebro-vascular events. The events that are adjudicated and the adjudication process will be detailed in the Cardiovascular Adjudication Committee Charter. Dedicated eCRFs will be used for events of myocardial infarction-unstable angina, stroke-transient ischemic attack, and death. In addition, the site may be contacted for additional source documentation for relevant events.

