1. Visit 1 of this LT extension study should preferably be performed in one visit combined with the last visit of the preceding trial 1311.6 or during the interim period of maximum 5 days after completion of the last visit in 1311.6. If an EoT colonoscopy has not been performed during E1 within 1311.6, it must be performed between V1 and V2 in 1311.20/M15-989.
2. Assessments performed at the last visit in the previous trial do not have to be repeated at visit 1 in this trial. Assessments scheduled but not performed at the last visit in the previous trial should be repeated at Visit 1 in this trial, and the results entered into the CRFs of both trials 1311.6 and 1311.20/M15-989.
3. For patients who discontinue study medication before scheduled EoT visit, an early EoT visit should be performed. After last dose of study medication, a 140 day follow-up call should be scheduled. Upon EC/CA approvals of Study M16-000 protocol amendment 4, patients receiving treatment in M15-989 will have the option to enroll into M16-000 Sub-Study 3 after completing the EoT visit.
4. Must be performed at Visit 1 and starting from Visit 2 prior to each study drug administration in females of childbearing potential. In case of positive result, serum pregnancy test will be performed. Study drug will only be administered if pregnancy is ruled out.
5. Positive QuantiFERON-TB Gold In-Tube tests need not to be repeated. If TB or infection is suspected at any time during the study, a routine work up including chest x-ray and a QuantiFERON-TB Gold In-Tube test or an infection assessment must be performed at investigator's discretion and according to local guidelines.
6. Assessment of AE after subcutaneous injections will also include assessment of local tolerability. The assessment of local tolerability should be done just before the patient leaves the investigator site.
7. All assessments are to be completed prior to study drug administration, unless otherwise specified.
8. An end of trial call should be performed for both patients that agree to enroll into M16-000 Sub-Study 3 OLE or those that do not choose to participate.
9. For details of laboratory tests see [Section 5.2.3](#), [Table 5.2.3:1](#) and [Table 5.2.3:2](#).

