3.3.3 Exclusion criteria

Patients meeting any of the following criteria cannot roll over.

1. Patients who were not compliant with key study procedures (colonoscopy, treatment compliance, endpoint assessment, contraception measures) in preceding trial 1311.6
2. Patients who could not tolerate BI 655066/ABBV-066 (risankizumab) treatment for tolerability or safety reasons in the preceding trial
3. Are pregnant, nursing, or planning pregnancy while enrolled in the study, or within 20 weeks after receiving the last dose of study medication.
4. Patients must agree not to receive a live virus or bacterial or BCG vaccination during the study or up to 12 months after the last administration of study drug.

5. Patients who have developed malignancy, or suspicion of active malignant disease during the preceding trial.
6. Are intending to participate in any other study using an investigational agent or procedure during participation in this study.
7. Cannot adhere to the concomitant medication requirements mentioned in [Section 4.2.2.](#)

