3.3.4 Removal of patients from therapy or assessments

3.3.4.1 Removal of individual patients

An excessive rate of withdrawals may render the study results uninterpretable; therefore unnecessary withdrawal of patients must be avoided. Patients who discontinue their treatment early should undergo all study required procedures including an early EoT visit and colonoscopy, as defined in [Section 6.](#)

Patients have the right to withdraw from the study at any time without the need to justify the decision.

The sponsor reserves the right to terminate a patient from the trial for non-compliance.

The investigator has the right to remove patients from the study for non-compliance.

Furthermore, patients' treatment must be discontinued early due to lack of efficacy (defined as an endoscopically confirmed CDAI re-increase to >100 points above baseline in 1311.6 and a CDEIS >4), or for other reasons (as described below). If, in the investigator's opinion, such a patient requires alternative medical therapy for their Crohn's disease, the study treatment must be stopped and patients may receive conventional treatment for active disease as per investigator's judgment.

Criteria and rules for stopping patient treatment due to reasons other than lack of efficacy include:

- Development of a toxicity or adverse event which warrants drug discontinuation.
- Development of any potentially life-threatening toxicity.
- Any concomitant illness that prevents compliance.
- The patient is unwilling to continue in the trial.

- Pregnancy in a female participant.
- Patient lost to follow-up despite reasonable efforts to make contact with the patient.
- Patient is no longer able to participate for other medical reasons (e.g., surgery, adverse events or other diseases).
- The DMC may recommend termination or re-design of the trial for other relevant issues of safety.

Patients who discontinue from the study after Visit 2 will be considered as "early discontinuations" and the reason for premature discontinuation must be recorded in the eCRFs. The data will be included in the trial database and will be reported.

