Patients showing these lab abnormalities need to be followed up according to [Section 10.1.2](#) of this clinical trial protocol and the hepatic injury adverse event form provided via EDC system. These lab findings constitute a hepatic injury alert and the patients showing these lab abnormalities need to be followed up according to the hepatic injury AE form via the EDC-system. In case of clinical symptoms of hepatic injury (icterus, unexplained encephalopathy, unexplained coagulopathy, right upper quadrant abdominal pain, etc.) without lab results (ALT, AST, total bilirubin) available, the investigator should make sure these parameters are analysed, if necessary in an unscheduled blood test. Should the laboratory results meet the definition of hepatic injury, the investigator will complete the supplemental form. **Cardiac Events/Procedures**

In the case of any of the following reported major cardiovascular adverse events (MACE), the appropriate supplemental eCRFs should be completed:

- Cardiac events;
- Myocardial infarction or unstable angina;
- Cerebral vascular accident and transient ischemic attack;
- Cardiovascular procedures

Tuberculosis (TB)

In the case of any positive TB test or diagnosis of active TB, the appropriate supplemental eCRF should be completed.

Intensity of adverse event

The intensity grading of AEs will be performed according to Rheumatology Common Toxicity Criteria (RCTC) Version 2.0 developed by OMERACT ([R13-3515](#)). See [Appendix 10.3](#) for intensity/severity classification.

Causal relationship of adverse event

The definition of an adverse reaction implies at least a reasonable possibility of a causal relationship between a suspected medicinal product and an adverse event. An adverse reaction, in contrast to an adverse event, is characterised by the fact that a causal relationship between a medicinal product and an occurrence is suspected.

Medical judgment should be used to determine the relationship, considering all relevant factors, including pattern of reaction, temporal relationship, de-challenge or re-challenge,

confounding factors such as concomitant medication, concomitant diseases and relevant history.

Arguments that may suggest that there is a reasonable possibility of a causal relationship could be:

- The event is consistent with the known pharmacology of the study drug.
- The event is known to be caused by or attributed to the drug class.

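### Section 2.3 bars patients with infection or untreated TB, but the exclusion list does not, and no stopping rule follows a positive TB test

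*Protocol*

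**What the plan says.** Protocol Section 2.3 makes three statements about infection risk:

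- On infection at entry, it says "Patients having current signs or symptoms of infection or history of serious infection will not be included in the study".
- On TB at entry, it gives the purpose of the Visit 1 interferon-gamma release assay as "to exclude or discontinue patients with untreated active or latent TB infection".
- On TB during treatment, it plans a yearly repeat of the assay for those who were negative at the start, with the aim of ruling TB out.

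The operative sections read as follows:

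- **Section 3.3.3** opens with "Patients meeting any of the following criteria cannot roll over" and lists seven criteria. None concerns infection or TB. The three inclusion criteria in Section 3.3.2 do not mention them either.
- **Section 3.3.4.1** begins its list with "Criteria and rules for stopping patient treatment due to reasons other than lack of efficacy include" and names neither TB nor a positive TB test.
- **Footnote 5 of Flow Charts 1 to 3** says "Positive QuantiFERON-TB Gold In-Tube tests need not to be repeated". It asks for a work-up if TB or infection is suspected, at the investigator's discretion and under local guidelines.
- **Section 5.2.2.1** says "In the case of any positive TB test or diagnosis of active TB, the appropriate supplemental eCRF should be completed".

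**The concern.** Section 2.3 argues that the risk of an immune-modulating drug is acceptable partly because infected patients are kept out and untreated TB leads to exclusion or discontinuation. Sites screen from the eligibility lists and stop treatment from the removal criteria. If those lists do not carry the safeguards, the benefit-risk argument rests on protections that nobody is instructed to apply.

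There are two gaps. At entry, a patient with a current infection, a history of serious infection or untreated TB meets no listed exclusion. On treatment, the yearly re-test can turn positive with no stated effect on dosing. Long-term safety is the primary objective, and Section 7.3.3 names serious infection as a main focus of the safety analysis, so both the patients and the main result are exposed.

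**Working it through.** This is mainly a comparison of texts, followed by a count of scheduled doses.

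**Step 1: entry.** The seven exclusions in Section 3.3.3 cover non-compliance in 1311.6, intolerance in 1311.6, pregnancy or nursing, live vaccination, malignancy, participation in another investigational study, and the concomitant medication rules. Infection or TB: 0 of 7. Section 3.3 bases the eligibility check on successful treatment in 1311.6 and consent. Section 6.2.1 describes a check based on CDAI. Neither refers to the infection conditions of Section 2.3.

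**Step 2: on treatment.** No stopping reason in Section 3.3.4.1 names TB. The nearest are an adverse event that warrants discontinuation and other medical reasons, and both depend on judgement. Under Section 5.2.2.1 a laboratory abnormality counts as an adverse event only if it leads to discontinuation, needs therapeutic intervention, or the investigator considers it one. A symptom-free conversion that is left untreated meets none of these automatically, yet untreated TB is the case Section 2.3 is concerned with.

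**Step 3: comparison with pregnancy.**

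| Element | Pregnancy | TB |
|---|---|---|
| Exclusion in 3.3.3 | Yes | No |
| Named stopping reason in 3.3.4.1 | Yes | No |
| Dosing rule in a flow chart footnote | Yes (footnote 4) | No (footnote 5) |
| Mandatory discontinuation in 5.2.2 | Yes (5.2.2.2) | No |

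The protocol carries a safety condition through to the operative text for pregnancy but not for TB. That points to an omission.

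**Step 4: scheduled doses after a positive re-test.** The visits come from the SAP copy of the flow charts (SAP Section 4.2.1). The formula is: later doses = number of the last dosing visit minus number of the re-test visit. The dose at the re-test visit is not counted, on the assumption that the result arrives afterwards.

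| Re-test | Flow Chart 1 (last dose V27) | Flow Chart 2 (last dose V27) | Flow Chart 3 (last dose V30) |
|---|---|---|---|
| First | V8, wk 52: 27 − 8 = 19 | V8, wk 54: 27 − 8 = 19 | V10, wk 56: 30 − 10 = 20 |
| Second | V14, wk 100: 27 − 14 = 13 | V14, wk 102: 27 − 14 = 13 | V16, wk 104: 30 − 16 = 14 |
| Third | V20, wk 148: 27 − 20 = 7 | V20, wk 150: 27 − 20 = 7 | V21, wk 144: 30 − 21 = 9 |
| Fourth | V25, wk 188: 27 − 25 = 2 | V26, wk 198: 27 − 26 = 1 | V27, wk 192: 30 − 27 = 3 |

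**Sensitivity to the table reading.** The protocol's own late-visit tables are visibly broken in the extracted text. Taken literally, they put the late re-tests at V20 and V24 in Flow Chart 1 (27 − 20 = 7; 27 − 24 = 3) and at V20 and V25 in Flow Chart 3 (30 − 20 = 10; 30 − 25 = 5). On that reading the range widens from 7–9 to 7–10 for the third re-test and from 1–3 to 1–5 for the fourth.

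**The case against.** The strongest reply is that Section 2.3 is itself current protocol text in mandatory terms, and the trial must be run to the whole protocol. On that view the entry rule exists and is merely in the wrong place. A careful investigator could apply it, but the exclusion list presents itself as the list of who cannot roll over, and a site working from it would not meet the rule.

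Second, enrolment looks complete: the SAP describes roll-over in the past tense, and Amendment 4 closes the study early and offers a move to M16-000. This reduces the practical value of new exclusions. It does not affect the stopping rule for patients still receiving drug.

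Third, there are other safeguards. The stopping list is not exhaustive. Clinically relevant laboratory results are recorded as adverse events (Section 5.2.2.2). A positive test triggers a dedicated form, a DMC reviews safety data, and the SAP tabulates TB as an area of safety interest. A converter would therefore be visible, and active TB could be stopped by judgement. Visibility is still not an instruction about dosing.

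Fourth, Section 2.3 targets only untreated TB, and its reference to discontinuation is attached to the Visit 1 assay; for re-tests it says only that they serve to exclude TB. So a converter who is treated might properly continue. This is a fair limit on the dose counts, but it also shows that the protocol orders yearly tests without saying what follows from them.

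Finally, the feeder trial may have had its own infection exclusions; the documents do not say. Exclusion 2, for patients who could not tolerate the drug for safety reasons, would catch some serious infections there. Neither would reliably cover infection or TB acquired during 1311.6 or in the gap before roll-over, when Section 3.1 allows for anti-TNF or other biologic treatment subject to wash-out.

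**Conclusion.** The concern holds. Section 2.3 sets entry conditions for infection and TB that the eligibility criteria omit, and the yearly TB test has no stated consequence for dosing. The generic stopping reasons permit a stop but do not require one, and they do not reliably reach symptom-free latent TB.

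The number of patients affected cannot be derived from the documents. The scheduled exposure left open is at most 19 or 20 doses after a conversion at the first re-test and 13 or 14 at the second. On the SAP's tables it is 7 to 9 at the third and 1 to 3 at the fourth; the late figures depend on which copy of the flow charts is read. All assume that the full schedule is completed, no discretionary stop is made and TB is left untreated. Early closure shortens them. This should be corrected, with priority to the on-treatment rule.

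The finding is limited to what Section 2.3 promises. For infections other than TB it promises non-inclusion and adverse event monitoring, not discontinuation.

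**What to change.** 1. In Section 3.3.4.1, add a named reason to stop study drug: active TB, or latent TB that is not treated, found at yearly testing or at any other time. Limiting the latent TB rule to untreated cases keeps it in line with Section 2.3 and avoids losing treated patients.
2. Put the same rule into footnote 5 of Flow Charts 1 to 3, next to the sentence on not repeating a positive test, so that the test and its consequence are read together. Apply it to all patients still on treatment.
3. In Section 3.3.3, add exclusions for untreated active or latent TB, for current signs or symptoms of infection, and for a history of serious infection. If enrolment has closed, this mainly removes the contradiction with Section 2.3.

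The cost is wording in two sections and in one footnote repeated across three charts. The TB tests and the TB eCRF are already scheduled, so no new assessment is needed.
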